#### 10.0 DEVICE INFORMATION

#### 10.1 Mepitel Film

*Background:* Mepitel Film is a transparent film dressing designed to protect fragile and sensitive skin and minimize the risk of skin breakdown. It can be used alone or in combination with other products.

Formulation: Mepitel Film with Safetac® technology is available in a variety of different sizes (6 x 7 cm, 10 x 12 cm, 10 x 25 cm, 15 x 20 cm). Only the 10 x 25 cm and 15 x 20 cm sizes will be used for this study.

Preparation and storage: Store as directed.

Administration: Dry the skin/surrounding skin thoroughly. Remove the protection foil (printed Safetac®) to expose the adhesive. Position the dressing. Mepitel Film can be repositioned as long as the paper frame is intact. Remove the white paper frame. Do not stretch the dressing when applying. For best results, Mepitel Film shall overlap the dry surrounding skin by at least 5 cm for the larger sizes, in order to fixate securely. Firmly smooth out the dressing onto the skin. Mepitel Film can be removed without causing skin stripping and pain.

*Procurement:* Mepitel Film will be supplied in a kit and provided and shipped by the Mayo Clinic.

After receiving IRB approval for this study, each participating institution will order a supply of Mepitel Film from the Alliance by emailing the Alliance Mepitel Film Order Form to:

The A221803 Mepitel Film Kit Order Form can be found on the A221803 study page of the Alliance and CTSU websites. Site personnel should reorder additional Mepitel Film Kits based on their inventory levels, so that the Mayo Clinic staff may send additional supplies as needed. The initial supply should be sufficient to enroll additional patients at the site.

Within ninety days after the last patient is treated at the institution, any expired or remaining supplies should be destroyed according to institutional procedure.

Accountability

Sites should track receipt of the Mepital Film kits received from the Mayo Clinic and the quantity dispensed to patients. A Product Accountability Form can be found on the Alliance Website under A221803 *Supplemental Materials* or sites can choose to create their own form.

The Mepitel Film used in this study is subject to regulation by the FDA under an IDE application.

#### 11.0 MEASUREMENT OF EFFECT

# 11.1 Patient reported Measures

# 11.1.1 mRISRAS (Appendix VI)

After consideration of the various assessment tools, we selected the mRISRAS for its strength in both the PRO and provider assessed domains when assessing radiation dermatitis (see Section 1.6). Given the psychometric properties of the RISRAS were evaluated in 1999, as part of this study we will conduct psychometric testing of the mRISRAS.

The mRISRAS will be obtained at baseline (i.e. prior to the start of radiation), weekly during treatment, 7-14 days post treatment, and at the 3-month, 6-month, 1 year and 2-year follow-up visits. The PRO component of the mRISRAS will be evaluated for the primary endpoint, while the provider component and combined patient-provider scores will be evaluated as exploratory endpoints. The PRO section is feasible for the patient to complete in less than 5 minutes. Similarly, the provider scored component should take less than 5 minutes to complete. The mRISRAS is self-explanatory; however, when grading the erythema, the average erythema should be scored. More severe isolated areas of dermatitis will be accounted for with the additional domains, namely dry desquamation, moist desquamation, and necrosis.

# 11.1.2 PRO-CTCAE (See Appendix VIII)

To complement the primary endpoint, we will be collecting a short PRO-CTCAE questionnaire at baseline (i.e. prior to the start of radiation), weekly during treatment, 7-14 days post treatment, and at the 3-month, 6-month, 1 year and 2-year follow-ups. This questionnaire will include questions pertaining to radiation skin reaction, itching, general pain, and breast swelling and tenderness.

# 11.2 Site staff survey: Thin Film Clinical Utilization Survey (Appendix VIII)

This survey is not a validated metric but has been designed as a quick method for trained staff to track and record their experience in working with Mepitel Film (see Section 1.6). The survey tracks the frequency of film exchange, quantity of film used, incidence of film detachment, time and number of personnel required for exchange, and ease of use, allowing for descriptive reporting of these parameters. This survey should be completed once per week, prior to radiation therapy. It will take approximately 5 minutes to complete this survey. Recognizing that the application of Mepitel Film requires nursing/trained staff support, demonstration of its feasibility and ease of use will provide valuable data regarding its feasibility and generalizability. Furthermore, tracking the quantity of Mepitel Film used across patients will allow for an estimation of the average financial cost of this intervention.

# 11.3 Photographic assessment (Appendix III)

Baseline photographs will be obtained utilizing standardized views prior to the start of radiation, irrespective of the randomization arm. For patients randomized to the Mepitel Film arm, the photographs will be obtained prior to the application of Mepitel Film.

After completion of radiation, two additional sets of photographs will be obtained for patients randomized to the Mepitel Film Arm; one prior to the removal of Mepitel Film, and the second at least one hour after the removal of the Mepitel Film. These latter photographs will be used for analysis of one of the pre-specified secondary endpoints: a centralized, blinded, provider assessment of the maximum severity of radiation dermatitis. For patients randomized to the standard of care arm, only one set of photographs will be obtained immediately following completion of radiation therapy. Photographs will also be obtained at the 7-14-day follow-up 3-month, 6 months, 1 year and 2-year follow-up visits for all patients. In addition to providing a blinded assessment, adding a centralized analysis also addresses potential institutional disparities inherent in a multi-center trial.

We recognize one limitation in evaluating photographs obtained in multiple institutions may be the quality and conformity of the photographs themselves. Standardized views (Appendix III) are provided to help mitigate these potential differences. The provider-scored mRISRAS was selected for this secondary endpoint, to provide uniformity and easier comparisons across endpoints. We felt that acquiring weekly blinded photographs would be both overly burdensome on the patient and provider and is further complicated by the fact that Mepitel Film would need to be removed prior to acquiring photographs and replaced after acquisition. As such, photographs will only be acquired before and after radiation therapy, as well as at the follow up visits at 7-14 days, 3 months, 6 months, 1 year and 2 years after radiation. This analysis will allow for an objective, blinded, centralized analysis of the maximal grade of radiation dermatitis, further strengthening the institutionally scored secondary endpoint.

Specifically, de-identified digital photographs obtained at baseline and following the completion of radiation (following removal of Mepitel for patients randomized to the Mepitel Film arm), will be viewed by a blinded panel of providers on a computer monitor. The degree of radiation dermatitis will be graded according to the mRISRAS (see Section 11.1.1, Section 13.4.2, and Section 13.5.2).

# 11.4 Psychometric Testing of mRISRAS

Comparative psychometric analysis of the mRISRAS will be carried out by procedures established by Huschka et al. In brief, we will carry out simple correlational analyses followed by Bland-Altman procedures after translating the patient reported outcome measures onto a

common 0-100 scale. We will also carry out a responsiveness analysis using the methods of Stockler and Guyatt.

An expanded panel of providers assembled for the blinded assessment of radiation dermatitis, comprised of physicians and nurses (see Section 11.3) will also be provided with standardized images representing the various grades of radiation dermatitis. Providers will be asked to score the blinded images, at two different time points. We will use these assessments to evaluate both intra-rater reliability as well as inter-rater reliability. In addition to photos, the panel will also be provided with questions appropriate for validation, which will be used to analyze the face and content validity of the mRISRAS.

# 11.5 Criteria for Disease Response

Local and regional recurrences: A recurrence will be classified as local if it recurs on the chest wall (local) or reconstructed breast. Local regional recurrence will be classified for the axillary, supraclavicular, infraclavicular or ipsilateral internal mammary lymph nodes, and distant recurrence for elsewhere.

# 11.5.1 Local Recurrence

Local recurrence is defined as histologic evidence of ductal carcinoma in situ or invasive breast cancer in the ipsilateral reconstructed breast or chest wall.

# 11.5.2 Regional Recurrence

Regional recurrence is defined as the cytologic or histologic evidence of disease in the ipsilateral internal mammary, ipsilateral supraclavicular, ipsilateral infraclavicular and/or ipsilateral axillary nodes or soft tissue of the ipsilateral axilla.

#### 11.5.3 Distant Recurrence

Distant recurrence is defined as the cytologic, histologic and/or radiographic evidence of disease in the skin, subcutaneous tissue, lymph nodes (other than local or regional metastasis), lung, bone marrow, central nervous system or histologic and/or radiographic evidence of skeletal or liver metastasis.

#### 12.0 END OF TREATMENT/INTERVENTION

# 12.1 Duration of Protocol Treatment

Radiation therapy is to be given 5 days a week for 5-6 weeks. For patients randomized to Mepitel Film, the film will be applied prior to initiation of radiotherapy and will remain in place for up to 2 weeks following the completion of radiation. Please see the study calendar (Section 5.0) and the treatment section (Section 7.0) for treatment and follow-up time periods (Section 12.3).

#### 12.2 Criteria for Discontinuation of Protocol Treatment/Intervention

In the absence of treatment delays due to adverse event(s), treatment may continue until one of the following criteria applies:

Intercurrent illness that prevents further administration of treatment

Unacceptable adverse event(s)

Patient decides to withdraw from the study

General or specific changes in the patient's condition render the patient unacceptable for further treatment in the judgment of the investigator

Clinical progression

Patient non-compliance

Pregnancy

All women of child bearing potential should be instructed to contact the investigator immediately if they suspect they might be pregnant (e.g., missed or late menstrual period) at any time during study participation.

The investigator must immediately notify CTEP in the event of a confirmed pregnancy in a patient participating in the study.

The product manufacturer can no longer provide the study agent.

The reason(s) for protocol therapy discontinuation, the reason(s) for study removal, and the corresponding dates must be documented in the Case Report Form (CRF).

# 12.3 Follow-up

# 12.3.1 Duration of Follow-up

Patients will undergo scheduled follow-up assessments at 7-14 days, 3 months, 6 months, 1 year and 2 years post radiation, then physical exams every 6 months until 5 years post radiation. See study calendar (Section 5.0).

# 12.3.2 Follow-up for Patients who Stop Study Treatment/Intervention Early

Follow up for patients who stop due to toxicity: For patients who are willing to continue to be followed per protocol, the same schedule of weekly management visits during treatment will be followed, as well as the same follow-up schedule. Additionally, all adverse events will be recorded, and patients will be asked to complete questionnaires, as specified in the protocol. An Off-Treatment form will be completed at the time of discontinuation of the intervention, which will record toxicities at the time of discontinuation, as well as the reason for discontinuation as specified by the patient.

For patients who withdraw from the study for any reason: For these patients, an Off-Treatment Form will be completed, which will record toxicities at the time of discontinuation, as well as the reason for discontinuation as specified by the patient.

Follow up for patients who receive non-protocol therapy: For patients who receive non-protocol therapy, the type of therapy received will be recorded as well as the dates, and the patients will continue to be followed per protocol. This includes all pre-specified management visits, follow-ups, data collection as outlined in the protocol, and questionnaires.

# 12.4 Extraordinary Medical Circumstances

If, at any time the constraints of this protocol are detrimental to the patient's health and/or the patient no longer wishes to continue protocol therapy, protocol therapy shall be discontinued. In this event:

Document the reason(s) for discontinuation of therapy on data forms.

Follow the patient for protocol endpoints as required by the Study Calendar.

# 12.5 Managing ineligible patients and registered patients who never receive protocol intervention

#### **Definition of ineligible patient**

A study participant who is registered to the trial but does not meet all of the eligibility criteria is deemed to be ineligible.

Update #03

# Follow-up for ineligible patients who continue with protocol treatment

Patients who are deemed ineligible after registering may continue protocol treatment, provided the treating physician, study chair, and executive officer agree there are no safety concerns if the patient continues protocol treatment. All scans, tests, and data submission are to continue as if the patient were eligible. Notification of the local IRB may be necessary per local IRB policies.

# Follow-up for ineligible patients who discontinue protocol treatment

For patients who are deemed ineligible after registering to the trial, who start treatment, but then discontinue study treatment, the same data submission requirements are to be followed as for those patients who are eligible and who discontinue study treatment.

# Follow-up for patients who are registered, but who never start study treatment

For all study participants who are registered to the trial but who never receive study intervention (regardless of eligibility), the follow-up requirements are specified below.

Baseline, off treatment, and post-treatment follow up (i.e., relapse, progression, and survival) data submission required. See the Data Submission Schedule accompanying the All Forms Packet.

#### 13.0 STATISTICAL CONSIDERATIONS

# 13.1 Study Design

This is a randomized, controlled clinical trial to determine the ability of Mepitel Film to reduce the severity of radiation dermatitis in patients undergoing post-mastectomy radiotherapy for breast cancer when compared with the existing institutional standard of care. Patients will be randomized in a 2:1 ratio to receive either Mepitel Film or the existing institutional standard of care. The 2:1 randomization favoring Mepitel Film was chosen to aid in recruitment given an expected enthusiasm for Mepitel Film based on previously published series. Randomization will be stratified on the basis of a breast reconstruction (yes; no), planned boost (yes; no), planned bolus (yes; no), and according to 3 levels of BMI, consistent with the established cut-offs as defined by the WHO (< 25; 25-29.99; and  $\ge 30$ ).

# 13.2 Description of Randomization Routine

After a patient is registered they will be assigned to one of the two arms (Mepitel Film; existing institutional standard of care) in a 2:1 ratio utilizing a dynamic allocation algorithm based on the methods by Pocock and Simon. The goal of the algorithm is to maintain arm balance with respect to the aforementioned stratification factors. In order to ensure that arm assignment is not deterministic, a level of randomness has been added to the algorithm such that patients will be assigned to the arm that leads to more imbalance 10% of the time. Dynamic allocation is a common approach in cancer clinical trials where we desire arms to be balanced across several prognostic factors. The method is considered robust because it ensures excellent arm balance overall and within the stratification factor levels, even with a large number of stratification factors 

# 13.3 Sample Size, Accrual Time, and Study Duration

Our statistical plan is informed by the largest single-institution, randomized, intra-patient-controlled study of Mepitel Film to date. This trial evaluated 78 patients receiving radiation therapy for breast cancer in which all patients had a portion of skin in the treatment field covered by Mepitel Film. Based on the combined patient- and provider-completed mRISRAS scores, utilization of Mepitel Film demonstrated a substantial 92% reduction in the extent of radiation-induced skin reactions, compared to an adjacent area of skin treated with aqueous cream. 42 The

findings translated into a large (> 0.80) effect size providing a benchmark used to guide our study's power analysis. The prophylactic effect was more marked, when based solely on the patient-completed mRISRAS scores. We expect the effect size will be attenuated given the multi-institutional nature of our study and due to the anticipated heterogeneity in the use of skin care products within our existing institutional standard of care arm, corresponding to a medium effect size of 0.5. An effect size of 0.5 is considered clinically relevant for our patient population receiving radiation therapy, and who are at risk for acute radiation dermatitis, which may compromise quality of life. Further, such an effect size has also been suggested to be clinically significant in general for patient-reported quality of life outcomes in cancer populations.

Based on the aforementioned single-institution study, the distribution of the combined patient-and provider-completed mRISRAS scores (averaged over the post-randomization assessments) were positively skewed. As such, we propose using the AUC to summarize the sequence of repeated patient-completed mRISRAS scores for each patient. This summary measure tends to be approximately normally distributed. We hypothesize that the Mepitel Film arm will be associated with an improved AUC summary measure, corresponding to decreased patient-completed mRISRAS scores compared with institutional standard of care. With 192 patients randomized in a 2:1 ratio (128 Mepitel Film; 64 existing institutional standard of care), the study will have at least 90% power for a two-sample t-test to detect an effect size of -0.5 (Mepitel Film vs institutional standard of care) based on the AUC summary measure with a two-tailed alternative and a 5% Type I error rate. These results assume that two sequential tests are made using the O'Brien-Fleming spending function (see Section 13.4.3).

We anticipate that up to 10% of patients will not have met the eligibility criteria and/or not have submitted any mRISRAS data, and thus the target sample size will be inflated to 216 patients (144 Mepitel Film; 72 existing institutional standard of care). Importantly, any placement of the Mepitel Film will make the patient evaluable for the primary analysis provided that the patient had at least one patient-completed mRISRAS score, and was randomized (See Section 13.4.2 and the definition of the full analysis set).

Using conservative estimates, based on the Alliance Community Interest and Feasibility Survey conducted in May of 2018, we anticipate an accrual rate of 9 patients per month; therefore, to achieve the targeted accrual of 216 patients we anticipate that the accrual period will be approximately 24 months. Since the last protocol scheduled follow-up visit is 60 months post-radiation therapy, the corresponding total study duration will be approximately 84 months.

Because African American and Hispanic women may experience more significant acute toxicities we will make a concerted effort to accrue 25% (or 54 of 216) of the total patients in this combined category. Details on how we will achieve this important accrual goal are found in Section 13.9. Despite these efforts, if we still have not accrued 54 African American and Hispanic women once our study meets its planned accrual goal of 216 patients, we will close it to further accrual, with the exception of accruing the remaining Hispanic and African American women for a total of 54 such women. The justification for targeting a sample of 54 African American and Hispanic women and the analysis plan for this subpopulation is described in Section 13.9.

# 13.4 Statement for Primary Endpoint

# 13.4.1 Primary Endpoint

The primary endpoint is the serially measured patient-completed mRISRAS scores obtained at baseline (i.e. prior to the start of radiation), during weekly radiation therapy, at  $10 \ (\pm \ 4)$  days post-radiation therapy, and at 3-months post-radiation therapy (Appendix VI). The primary endpoint was selected to assess the ability of Mepitel Film to impact

acute radiation dermatitis, which is defined as the skin toxicity secondary to radiation therapy that develops no later than 3 months post-radiation therapy. Moreover, the primary endpoint was chosen as a result of multiple discussions with the National Cancer Institute and National Cancer Institute reviewers. At a given time point, a patient-completed mRISRAS score ranges from 0 to 12, obtained from summing the 4 individual scores, where higher scores correspond to increased radiation-induced skin reactions. We anticipate that all patients will present with normal or near-normal skin based on the patient-completed mRISRAS score, corresponding to a baseline patient-completed mRISRAS score of < 4.

# 13.4.2 Analysis Plan for Primary Endpoint

The primary analysis will be based on the full analysis set, defined as all patients who were randomized and had at least one patient-completed mRISRAS score; furthermore, these patients will be analyzed in the arms to which they were randomized. Omitting patients from the primary analysis who do not provide any patient-completed mRISRAS data is not anticipated to cause any bias. The fact that patients do not provide any patient-completed mRISRAS data should be unrelated to the interventions to which patients were assigned. Furthermore, including a patient who does not provide any patient-completed mRISRAS data is not meaningful for analysis because the patient will not have a relevant contribution to the patient-reported outcome (PRO) estimate . Nonetheless, any potential bias arising from the exclusion of randomized patients who do not provide any patient-completed mRISRAS data will be fully investigated (see Section 13.7)

In order to adjust for the stratification factors in the primary analysis, the AUC will be computed for the prophylactic arms based on estimated parameters from a repeatedmeasures (means) mixed model. The outcome measures used in the repeated-measures (means) mixed model are the serially measured patient- completed mRISRAS scores obtained at baseline (i.e, prior to the start of radiation), weekly during radiation therapy, at  $10 (\pm 4)$  days post-radiation therapy, and at 3-months post-radiation therapy. The covariates included in the model are indicator variables for all assessment time points, an indicator for the prophylactic method, the corresponding interaction terms, and the four stratification factors. This analytic approach, which is a likelihood method, to compare the prevention of radiation-induced dermatitis between the two prophylactic methods will preserve the full analysis set, allow for missing data (i.e. under the reasonable assumption of missing at random), and account for important covariates. Furthermore, it has been shown that this analytic approach is superior to a simple AUC summary measure in terms of both bias and precision.  Because of the gains in precision, the power analysis described in Section 13.3 is conservative; i.e. the power associated with the repeated-measures (means) mixed model will be greater since the addition of all available patient-completed mRISRAS scores will provide more information. We will report the summary statistic AUC for each arm, including the respective 95% confidence intervals, as well as the difference in AUC between the two arms along with the 95% confidence interval for the true, but unknown difference; the difference in AUC between arms will be estimated from the repeatedmeasures (means) mixed model and contrast for the summary statistic AUC. Further the two-sided *P*-value testing the null hypothesis of no difference  $(H_0: \mu_{AUC_1} = \mu_{AUC_0})$  versus the two-sided alternative hypothesis that there is a difference  $(H_a: \mu_{AUC_1} \neq \mu_{AUC_0})$  will be obtained from the repeated-measures (means) mixed model. Provided that the difference in AUC achieves statistical significance at the 5% level, the primary objective will have been met.

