### In addition:

- Women of reproductive potential should agree to use an appropriate method of birth control throughout the duration of radiation due to the teratogenic potential of the radiation utilized in this trial.
- Patients must be available to initiate thin film usage before the start of radiation (same day or earlier), if randomized to the Mepitel Film arm.

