# 9.2 CTCAE Routine Reporting Requirements

In addition to the solicited adverse events listed in Section 9.1, the following table outlines the combinations of time points, grades and attributions of AEs that require routine reporting to the Alliance Statistics and Data Center. Questions about routine reporting should be directed to the Data Manager.

Combinations of CTCAE Grade & Attribution Required for Routine AE Data Submission on Case Report Forms (CRFs). Attribution may be secondary to radiation, and/or Mepitel Film.

Of note, pruritus is a common acute toxicity observed secondary to radiation and can also develop in response to Mepitel Film. Based on Mayo institutional experience, pruritus due to Mepitel Film is generally seen within the first week of use.

Attribution	Grade 1	Grade 2	Grade 3	Grade 4	Grade 5
Unrelated			a	a	a
Unlikely			a	a	a
Possible		a	a, b	a, b	a, b
Probable		a	a, b	a, b	a, b
Definite		a	a, b	a, b	a, b

- a) Acute Adverse Events: Other CRF Applies to AEs occurring between registration and within 90 days of the patient's last treatment date, or as part of the Clinical Follow-Up Phase.
- b) Chronic Adverse Events: Late CRF Applies to AEs occurring greater than 90 days after the patient's last treatment date.

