# 13.4.5 Planned Supplemental Analyses for Primary Endpoint

To further assess the robustness of the results obtained from the primary analysis, a supplemental analysis is planned. We will conduct longitudinal modeling of the patientcompleted mRISRAS scores through 3-months post-radiation therapy. We anticipate that all patients will present with normal or near-normal skin based on the patient-completed mRISRAS score, corresponding to a baseline patient-completed mRISRAS score of < 4. The baseline patient-completed mRISRAS scores will be retained as part of the response vector. Furthermore, we will assume that the mean patient-completed mRISRAS scores in each arm are equal at baseline. Stated differently, the longitudinal model will include indicators for time (baseline being the reference level for time) and the interaction between arm and time, but no main effect of arm. The focus in this analysis will be on the interaction effect, which concerns arm comparisons of the patterns of changes in the mean patientcompleted mRISRAS scores. In addition to plotting the model-based mean response profiles by arm, we will report each time-specific comparison between arms with a 95% confidence interval. Because arm assignment is random, constraining the randomization arm means at baseline to be equal will, in general, be more powerful than including the arm main effect and making no assumptions about arm differences in the mean response at baseline. Also this modeling approach for adjusting for baseline incorporates all available data at baseline, and at subsequent post-baseline time points in the analysis, despite the fact that some patients may be missing baseline patient-completed mRISRAS scores. This would not be the case if we analyzed the post-baseline patient-completed mRISRAS scores

and made no adjustment for the baseline patient-completed mRISRAS scores by including it as a covariate.

To further assess the robustness of the results obtained from the longitudinal model, the following covariates will be included: the four stratification factors, and reconstructed breast size, separation, and modality of boost. Unstructured covariance will initially be used, though alternative covariance structures (e.g. compound covariance) will be investigated with the final covariance structure selected based on minimization of the Akaike information criterion.

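### The primary AUC contrast is not adjusted for the baseline score, although the plan itself describes the equal-baseline model as generally more powerful

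*Combined protocol and SAP*

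**What the plan says.** In 13.4.2 the outcomes are the patient-completed mRISRAS scores at baseline, weekly during radiation, about 10 days after it and 3 months after it. On the mean structure the section says: "The covariates included in the model are indicator variables for all assessment time points, an indicator for the prophylactic method, the corresponding interaction terms", followed by the four stratification factors. The arm difference is obtained from this model through a "contrast for the summary statistic AUC". No baseline covariate and no equality constraint at baseline is listed. The sensitivity analyses in 13.4.4 do not add either one.

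Section 13.4.5 sets out a supplemental longitudinal model for the same scores. It drops the arm main effect and takes the baseline means as equal. The reason given is that "constraining the randomization arm means at baseline to be equal will, in general, be more powerful than including the arm main effect" and leaving baseline differences unrestricted. Its focus is the arm-by-time interaction. For reporting, the section says "we will report each time-specific comparison between arms", with confidence intervals; it specifies no AUC contrast.

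On the likely baseline scores, 13.4.1 says: "We anticipate that all patients will present with normal or near-normal skin", which it equates with a score below 4 on the 0 to 12 scale.

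**The concern.** With an arm indicator and all arm-by-time terms, every visit, baseline included, has a free mean in each arm. With complete data the AUC contrast is then a weighted sum of the differences in arm means, adjusted only for the stratification factors. Baseline scores can help to predict missing later scores under missing at random. Being in the response vector does not make them adjust the arm comparison.

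Two things are lost. The first is the precision that the correlation between baseline and later scores would give. The second is protection against a chance baseline difference, which feeds into the AUC difference mainly through that correlation.

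The form that 13.4.5 describes as less powerful is the form of the primary model. The primary test also gates the family of three secondary endpoints in 13.5.2, and two of those repeat this model, so the weakness carries over.

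**Working it through.** **Inputs from the documents.** 192 patients, 128 versus 64; effect size 0.5; two-sided 5% (13.3); final level 0.049 (13.4.3).

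**Assumptions, because the documents do not give them.** Complete data. Trapezoid AUC over days 0, 7, 14, 21, 28, 35, 45 and 126. Later scores have SD 1 and a common correlation of 0.45 to 0.75 with each other. Baseline SD is 0.4 to 1.0 times the later SD. Correlation ρ of baseline with each later score is 0.05 to 0.3. Stratification factors are left out.

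**1. The plan's own figure.** The standardised signal is 0.5 × √(128 × 64 / 192) = 3.266, so power = Φ(3.266 − 1.96) = 0.904. The exact t-test gives 0.901 at 0.05 and 0.900 at 0.049. The stated 90% is reproduced. It takes no credit for baseline.

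**2. Weights.** The trapezoid weights are 3.5, 7, 7, 7, 7, 8.5, 45.5 and 40.5, which sum to 126. Baseline has 3.5 / 126 = 2.8%, so any gain comes almost wholly through ρ.

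**3. Variance of the contrast under each model.** Write w₀ for the baseline weight, w for the later weights, s for the baseline SD, S for the covariance of the later scores and c for their covariance with baseline.

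- Free baseline means: w′Sw + 2w₀(w′c) + w₀²s².
- Equal baseline means: w′Sw − (w′c)²/s².

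**4. Worked case: ρ = 0.2, correlation among later scores 0.5, s = 0.5.** The later weights sum to 122.5 and their squares to 3978.75.

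- w′Sw = 0.5 × 122.5² + 0.5 × 3978.75 = 9492.5.
- w′c = 0.2 × 0.5 × 122.5 = 12.25.
- Free: 9492.5 + 2 × 3.5 × 12.25 + 3.5² × 0.25 = 9581.3.
- Equal: 9492.5 − 12.25² / 0.25 = 8892.25.
- Ratio 0.928; power = Φ(3.266 / √0.928 − 1.96) = 0.924.

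**5. Full range.** Extra patients = 192 / ratio − 192.

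| ρ | Variance ratio | Power (from 0.904) | Equivalent extra patients |
|---|---|---|---|
| 0.05 | 0.990–0.995 | 0.905–0.907 | 1–2 |
| 0.1 | 0.973–0.985 | 0.908–0.912 | 3–5 |
| 0.2 | 0.914–0.946 | 0.919–0.927 | 11–18 |
| 0.3 | 0.824–0.882 | 0.935–0.949 | 26–41 |

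Simulation (4000 trials per case, s = 0.5, correlation among later scores 0.5) gave ratios of 0.98 at ρ = 0.1 and 0.84 at ρ = 0.3. The adjusted and unadjusted estimates centred on the same effect.

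**6. Variations.**

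- If ρ starts at 0.3 and falls 10% or 20% per visit (correlation among later scores 0.45), the ratio is 0.921–0.932 or 0.963–0.970. Power is then only about 0.91 to 0.93.
- If the AUC starts at week 1, the ratio runs from 0.996–0.997 (ρ = 0.05) to 0.851–0.890 (ρ = 0.3), and power from 0.905 to 0.943. The point does not depend on where the AUC starts.

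**7. Chance imbalance.** The SE of the effect size is 1 / √(128 × 64 / 192) = 0.153, so a 2-SE baseline difference is 0.31 baseline SD. The contrast moves 0.12–0.17 SE per SE of baseline difference at ρ = 0.1, and 0.34–0.42 SE at ρ = 0.3. Multiplying by 2 × 0.153 gives a shift in effect size of 0.04–0.05 at ρ = 0.1 and 0.11–0.13 at ρ = 0.3.

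**The case against.** The strongest reply is that both models are valid, the stated power is met, and the gain may be trivial. Patients are expected to start with near-normal skin, and 3.2.6 excludes rash or dermatitis in the field. A floor effect would put the trial at the low end of the table. The stratification factors are already in the model and may absorb some of the correlation. All of this stands. It limits the size of the point but does not remove it. The instrument also asks about tenderness and pain, and 7.0 lets radiation begin 21 days after surgery, so some baseline spread is plausible.

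A second reply is that the remark in 13.4.5 concerns interaction terms, where the constraint helps more. That is fair. At ρ = 0.1 and s = 0.5, the variance of a single visit's change contrast falls from 1 + 0.25 − 2 × 0.1 × 0.5 = 1.15 to 1 − 0.1² = 0.99, or 14%, against about 2% for the AUC. The plan does not contradict itself, but the direction is the same for the AUC.

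A third reply is that the constraint adds an assumption that could fail here. Film may go on before the day radiation starts (3.1), while 11.1.1 requires only that the baseline score precede radiation. Section 9.2 notes that "pruritus due to Mepitel Film is generally seen within the first week of use", and itch is a scored item. If film raised the baseline score by 0.2 baseline SD, the constrained contrast would favour film by an effect size of 0.01–0.03 at ρ = 0.05–0.1 and 0.04–0.08 at ρ = 0.2–0.3. This is a real risk, and the change needs a safeguard against it.

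Finally, 13.4.5 would already show a baseline-driven result visit by visit. It would not correct the test that decides the trial.

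**Conclusion.** The concern holds. The primary contrast makes no use of a collected baseline score for adjustment, and the plan relegates the more efficient form to a supplemental analysis. The consequence is lost efficiency and conditional imbalance only. Power would rise from about 0.90 to between 0.905 and 0.949 for ρ of 0.05 to 0.3, with the upper end requiring a correlation that does not fade over follow-up. Near-zero baseline scores would make the gain negligible. These figures rest on assumed visit times, weights and correlations. The change is worth making because unadjusted power is 0.900 to 0.904, with little reserve, and the cost is small. Confidence is medium, since the correlation is unknown.

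**What to change.** In 13.4.2, take the AUC contrast from the model form of 13.4.5: time indicators, arm-by-post-baseline-time interactions, no arm main effect, and the four stratification factors. Write the AUC time weights and first time point into the contrast at the same time. Keep the current unconstrained model as a sensitivity analysis.

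Make the change before any comparison by arm is seen, including the interim analysis in 13.4.3. The documents do not show whether that analysis has taken place.

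To protect the equal-baseline assumption, have the baseline mRISRAS completed before the first film application, as 7.2.2 already requires for photographs. For patients already enrolled, check and report the order of score and film. Set any baseline score taken after film to missing, which the 13.4.5 model accommodates. This rule would affect only the film arm, so report how many scores it removes.

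The cost is a rewording of 13.4.2, one added contrast and a short clarification of when the baseline questionnaire is completed. The sample size does not change.
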